##### Categorical variables

Administration of corticosteroid therapy for irAEs

Administration of high-dose corticosteroid therapy for irAEs (prednisolone-equivalent of  $\geq 40$  mg)

Analysis content : The following aggregation will be performed for the endpoints:  
Summary statistics will be calculated for continuous variables.  
A frequency table (number of cases, percentage (%)) will be created for categorical variables.  
In addition, a frequency table (number of cases, percentage (%)) will also be created for the details of other drugs.

##### 【Division of categorical variables】

Factor	Category
Administration of corticosteroid therapy for irAEs	No; Yes; Unknown
Administration of high-dose corticosteroid therapy for irAEs	No; Yes

irAEs, immune-related adverse events

#### 7.2.2.9 Pre-treatment and treatment of infusion-related reactions caused by avelumab

Source : FAS, Efficacy analysis set

population

Endpoints : Presence or absence of premedication

Detailed name of the drug

Presence or absence of treatment and coping

PFIZER CONFIDENTIAL

CT24-WI-GL03-RF03 2.0 Non-Interventional Statistical Analysis Plan For Secondary Data Collection

Study 01-Jun-2020

Page 25 of 30

Analysis : A frequency table (number of cases, percentage (%)) will be created for the endpoints.

**【Division of categorical variables】**

Factor	Category
Presence or absence of premedication	No; Yes; Unknown
Presence or absence of treatment and coping	No; Yes; Unknown

**7.2.2.10 Subsequent treatment of avelumab plus axitinib combination therapy**

Source : FAS, Efficacy analysis set

population

Endpoints : Continuous variables

Second-line therapy period (days)

The period from the end date of first-line therapy to the beginning of second-line therapy (days)

Categorical variables

Performance of nephrectomy after avelumab plus axitinib combination therapy

Presence or absence of second-line therapy

Drug category

Second-line therapy regimen by drug category

Analysis : The following aggregation will be performed for the endpoints:  
content Summary statistics will be calculated for continuous variables.  
The period from the end date of first-line therapy to the beginning of second-line therapy (days) will also be estimated, considering the reason for termination of administration.  
A frequency table (number of cases, percentage (%)) will be created for categorical variables.

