9.2. Setting

This retrospective chart review will evaluate patient data derived from patient's existing medical records from the enrolled patients. All decisions regarding the clinical management and treatment of the patients are made by the investigator as part of standard care in a real-world setting and are not contingent upon the patient's participation in the study. Data will be collected at each study site (if available).

PFIZER CONFIDENTIAL

CT24-WI-GL02-RF02 4.0 Non-Interventional Study Protocol Template For Secondary Data Collection Study 01-Jun-2022

The study period is from 20 December 2019 to 31 October 2022. Patients with index date between 20 December 2019 and 17 October 2022 will be enrolled in this study. To ensure a 2 weeks follow up period, patients with an index date between 20 December 2019 and 17 October 2022 will be included in this study. The period of 2 weeks is determined based on the dosing interval for avelumab, in consideration of the fact that the start times of administration for avelumab and axitinib may differ.

- Index date: The date of first prescription of avelumab plus axitinib combination therapy.
- Observation period: Patients will be followed from the index date to 31 October 2022.

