9.3. Variables

Only data available from the treating physician's routine clinical assessments as per local standard of care will be collected. Variables and data sources are described in [Table 1](#). Detailed definitions will be included in the Statistical Analysis Plan (SAP).

Table 1. Variables in this study

Variable	Role	Data source(s)	Operational definition
Patient characteristics	Baseline characteristics, sub-group identifiers	Patient medical records	Patient characteristics at baseline, including the most recent data prior to initial treatment with avelumab plus axitinib: age, sex, height, weight, body mass index, smoking history, comorbidities, concomitant use of drugs, Eastern Cooperative Oncology Group (ECOG) performance status, pathological diagnosis (Fuhrman grade, TNM classification, histological type sarcomatoid component), the number of metastatic organs and the site of metastasis, the presence or absence of

PFIZER CONFIDENTIAL

CT24-WI-GL02-RF02 4.0 Non-Interventional Study Protocol Template For Secondary Data Collection Study 01-Jun-2022

			
nephrectomy, laboratory data (C-reactive protein (CRP), estimated glomerular filtration rate (eGFR), proteinuria), and International Metastatic RCC Database Consortium (IMDC) risk score
 
 - <1 year from time of diagnosis to systemic therapy - Karnofsky Performance Status <80% - Hemoglobin < lower limit of normal - Corrected calcium > upper limit of normal - Neutrophils > upper limit of normal - Platelets > upper limit of normal)
Avelumab plus axitinib treatment patterns	Exposure, outcome, sub-group identifier	Patient medical records	Start and end date of avelumab plus axitinib as first-line therapy.
Management of AE	Exposure, outcome, sub-group identifier	Patient medical records	Corticosteroid treatment for irAEs occurring during treatment with avelumab plus axitinib (drug, dose), the presence or absence of pre-medication and treatment for infusion-related reactions.
Subsequent treatment patterns	Exposure, outcome, sub-group identifier	Patient medical records	Subsequent treatment (drug name and duration of use for second-line therapy).
Clinical outcomes	Outcome	Patient medical records	
BOR, assessment of disease progression, real-world PFS, OS, ORR, TTD.
 
For the patients not nephrectomized at baseline: BOR for the primary lesion, the date of nephrectomy after administration of avelumab plus axitinib.

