**Study population**

*This retrospective chart review will evaluate patient data derived from the existing medical records of all enrolled patients. All decisions regarding the clinical management and treatment of the patients are made by the investigator as part of standard care in a real-world setting and are not contingent upon the patient's participation in the study. Data will be collected at each study site (if available).*

*The study period will range from December 20, 2019, to October 31, 2022. Patients with an index date between December 20, 2019, and October 17, 2022, will be enrolled in this study. To ensure a two-week follow-up period, patients with an index date between December 20, 2019, and October 17, 2022, will be included. The two-week follow-up period is determined based on the dosing interval for avelumab, considering that the time of initiation of avelumab and axitinib may differ.*

*Index date: The date of the first prescription of avelumab plus axitinib combination therapy.*

*Observation period: Patients will be followed-up from the index date to October 31, 2022.*

※ The date of the first prescription of avelumab plus axitinib combination therapy is the administration start date of the drug initiated first.

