*Study 01-Jun-2020*  
 Page 8 of 30

	record of death, the date when the survival of the patient was last confirmed on record (date of last hospital visit) will be used for censoring.
Time to treatment discontinuation (TTD) of avelumab plus axitinib combination therapy as first-line therapy	Defined as the period from the date of initiation of avelumab plus axitinib combination therapy to the date of ending treatment* for any reason (excluding discontinuation due to efficacy). In the case of discontinuation due to efficacy, the date of last administration will be used for censoring. If treatment has not ended, the date of the last hospital visit will be used for censoring. * The end date of treatment is the date of last avelumab administration + 13 days or the date of last axitinib administration, whichever occurs later, or the data-cut date, if performed earlier.
TTD of avelumab as first-line therapy	Defined as the period from the date of initiation of avelumab to the date of ending administration* for any reason (excluding discontinuation due to efficacy). In the case of discontinuation due to efficacy, the date of the last avelumab administration will be used for censoring. If treatment has not ended, the date of the last hospital visit will be used for censoring. * The end date of avelumab therapy is the date of the last avelumab administration + 13 days or the data-cut date, whichever occurs earlier.
TTD of axitinib as first-line therapy	Defined as the period from the date of initiation of axitinib to the date of ending administration* for any reason (excluding discontinuation due to efficacy). In the case of discontinuation due to efficacy, the date of the last axitinib administration will be used for censoring. If treatment has not ended, the date of the last hospital visit will be used for censoring. * The end date of axitinib is the date of the last axitinib administration.
Reasons for the TTD event	Reasons for TTD event are defined as follows: Disease progression/adverse event/other (death)/other (excluding death)
Reasons for censoring TTD	Reasons for censoring TTD are defined as follows: "Treatment ongoing" will be selected if the treatment is ongoing.

PFIZER CONFIDENTIAL

CT24-WI-GL03-RF03 2.0 *Non-Interventional Statistical Analysis Plan For Secondary Data Collection*  
 Study 01-Jun-2020  
 Page 9 of 30

	" discontinuation due to efficacy " will be selected in case of discontinuation due to efficacy.
--	--

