## 7 STATISTICAL METHODOLOGY AND STATISTICAL ANALYSES

### 7.1 STATISTICAL METHODS

#### Summary statistics

For summary statistics described in this plan, the following values will be calculated, unless otherwise specified:

Number of cases, number of missing cases, mean, standard deviation, minimum, quartiles, and maximum

PFIZER CONFIDENTIAL

CT24-WI-GL03-RF03 2.0 *Non-Interventional Statistical Analysis Plan For Secondary Data Collection*  
Study 01-Jun-2020  
Page 16 of 30

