**7.2.2.7 Treatment patterns for avelumab plus axitinib combination therapy as first-line therapy in a real-world setting**

Source : FAS, Efficacy analysis set

population

Endpoints : Continuous variables

Duration of treatment for avelumab plus axitinib (days)

Duration of treatment for avelumab (days)

Duration of treatment for axitinib (days)

Initial dose of avelumab [daily dose (mg)]

Initial dose of axitinib [daily dose (mg)]

Avelumab dose intensity (DI)

Axitinib DI

Axitinib relative DI (RDI)

Categorical variables

Initial dose of avelumab [daily dose (mg)]

Initial dose of axitinib [daily dose (mg)]

Presence or absence of changes in the avelumab dose

Presence or absence of changes in the avelumab dose (dose reduction)

Reason for changes in the avelumab dose (dose reduction)

Presence or absence of change in the avelumab dose (dose increase)

Termination of avelumab administration

Reason for termination of avelumab administration

Presence or absence of changes in the axitinib dose

Presence or absence of changes in the axitinib dose (dose reduction)

Reason for change in the dose of axitinib (dose reduction)

Presence or absence of changes in the axitinib dose (dose increase)

Termination of axitinib administration

PFIZER CONFIDENTIAL

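### Second-line treatment duration is summarised without censoring, so its reported median will be too short

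*SAP*

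**What the plan says.** Describing what patients receive after avelumab plus axitinib is a secondary objective (Protocol 8.2, SAP 2.2). Protocol Table 1 lists the data to be collected as "Subsequent treatment (drug name and duration of use for second-line therapy").

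SAP 7.2.2.10 analyses this in both the FAS and the efficacy analysis set. It names "Second-line therapy period (days") among the continuous variables and prescribes: "Summary statistics will be calculated for continuous variables". SAP 7.1 spells out that list as "Number of cases, number of missing cases, mean, standard deviation, minimum, quartiles, and maximum". The readable part of 7.2.2.10 has no event definition, no censoring rule and no count of ongoing courses.

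Follow-up has a fixed end. SAP 2.1 states: "Patients will be followed-up from the index date to October 31, 2022". Protocol 9.2 sets the same date. Index dates run from 20 December 2019 to 17 October 2022.

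First-line treatment is handled differently. For time to treatment discontinuation (TTD), SAP 5.1 says "If treatment has not ended, the date of the last hospital visit will be used for censoring", and SAP 7.2.2.6 uses Kaplan-Meier. SAP 7.2.2.7 also plans plain day counts such as "Duration of treatment for avelumab plus axitinib (days"), but these stand beside the censored TTD analysis.

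**The concern.** A second-line course that is still running on 31 October 2022 has a known start and an unknown end. Ordinary means, quartiles and medians need complete durations. Second line starts only after first line has stopped, so the time left to observe it is shorter than the follow-up from index, and many courses can be expected to be incomplete.

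The reported second-line duration would therefore depend partly on where the data cut fell. The same report would show a first-line duration that allows for censoring and a second-line duration that does not, and a reader could not properly set one against the other. Unlike first line, second line has no readable censored analysis to correct the impression.

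**Working it through.** **Figure to reproduce.** There is none. The documents give no second-line duration, no expected share ongoing and no expected number reaching second line.

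**Follow-up from the documents' dates** (SAP 5: 1 month = 30.4375 days)

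- Earliest index, 20 December 2019, to the cut: 1,046 days; 1,046 / 30.4375 = 34.37 months.
- Latest FAS index, 17 October 2022, to the cut: 14 days; 14 / 30.4375 = 0.46 months.
- Latest efficacy-set index (before 30 April 2022, so 29 April) to the cut: 185 days; 185 / 30.4375 = 6.08 months.

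**Direction.** Let D be the true second-line duration and R the time from second-line start to the cut, taken as independent.

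- Ongoing courses truncated at the cut: the recorded value is min(D, R), and P(min(D, R) > t) = P(D > t) × P(R > t) ≤ P(D > t). Its median cannot exceed the true median.
- Ongoing courses dropped: only courses with D ≤ R remain. The chance of being kept falls as D grows, so long courses are removed preferentially and the median falls.

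The direction is thus the same under either handling rule.

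**Size, by simulation.** Assumptions, none of them from the documents unless stated:

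- Follow-up C is uniform on 0.46 to 34.37 months (FAS) or 6.08 to 34.37 months (efficacy set).
- First-line duration T is exponential with median 8, 13.8 or 20 months. The 13.8 is the PFS median quoted in Protocol 7, borrowed only as a plausible value.
- If T < C, second line starts at once, so R = C − T.
- D is exponential with median 4, 8 or 12 months.

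This makes 2 × 3 × 3 = 18 scenarios. The mildest, a middle and the most severe are:

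| Set; first-line / true second-line median (months) | Ongoing at cut | Truncated median | Dropped median | Kaplan-Meier median |
|---|---|---|---|---|
| Efficacy; 8 / 4 | 19% | 3.41 (15% short) | 3.14 (21% short) | 4.0 |
| FAS; 13.8 / 8 | 41% | 5.1 | 4.5 | 8.0 |
| FAS; 20 / 12 | 54% | 6.18 (49% short) | 5.20 (57% short) | 12.05 |

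For the middle row, (8 − 5.1) / 8 is about 36% short and (8 − 4.5) / 8 about 44% short. Kaplan-Meier was within 0.12 months of the true median in all 18 scenarios.

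**Sensitivity.** In the FAS with a first-line median of 13.8 months, the assumptions were varied: front- or back-loaded accrual, Weibull shape 0.7 or 1.3, or a 1-month gap before second line. The shortfall was about 14% to 59% truncated and 16% to 70% dropped.

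**Second set of inputs.** A separate simulation used a median time to second line of 8, 12 or 18 months and true second-line medians of 3, 6, 9 or 12 months. It gave 14% to 54% ongoing, with a shortfall of 11% to 48% truncated and 16% to 56% dropped. In the FAS with 12 months to second line and a true median of 183 days, the results were 129 days truncated (29% short), 118 days dropped (35% short) and 182 days by Kaplan-Meier. In 3,000 simulated studies of 150 patients under those inputs (about 86 reaching second line, 33% of them ongoing), both plain medians were below the Kaplan-Meier median in every run.

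**The case against.** The strongest reply is that this is a descriptive study with no hypotheses, and that the second-line period can be read as observed exposure up to the cut rather than as an estimate of full treatment duration. The SAP keeps those two quantities apart for first line. On that reading, a clear label and a count of ongoing courses would be enough. However, 7.2.2.10 carries neither, and for second line there is no readable censored analysis to which a label could point.

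Parts of the SAP are blacked out, before the categorical derivations in section 5 and after 7.2.2.10. A derivation rule or a further analysis may sit there. A hidden rule could settle whether ongoing courses are truncated or dropped, but it would not remove the bias from the plain summary that is visibly planned. A hidden Kaplan-Meier analysis would answer the point, and the sponsor can check that at once.

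Two limits stand. The percentages rest on assumed durations, and a second-line median shorter than 4 months gives a smaller bias (11% in the mildest 3-month case). Also, Protocol Table 1 promises duration of use but does not show that an end date or an ongoing indicator was captured. Data collection was planned to end on 30 April 2023, before the SAP took effect on 22 May 2023, so this has to be confirmed in the database.

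**Conclusion.** The concern holds. As visibly planned, the median second-line duration is biased short whenever an appreciable share of courses is ongoing at the cut, and the staggered entry dates make that likely. The direction does not depend on how ongoing courses are recorded. The size does depend on unknown durations: 15% to 49% short if truncated and 21% to 57% short if dropped, given uniform accrual, exponential times, immediate second-line start and the medians assumed above. The mean and the other quartiles are affected as well. This should be corrected, but it touches one secondary descriptive variable and leaves the primary objective intact.

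**What to change.** In SAP 7.2.2.10, estimate second-line duration by Kaplan-Meier from the date second line began. The event is the end of second-line treatment; death on treatment ends it and counts as an event. Censor patients still on therapy at their last hospital visit on or before 31 October 2022. Report the median with its 95% confidence interval and the number still on second line at the cut.

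In SAP 7.2.2.7, keep the plain first-line day counts, label them as observed exposure to the data cut, and refer to 7.2.2.6 for treatment duration.

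The cost is one more Kaplan-Meier table and two lines of SAP text. The duration of second-line use is already collected. First confirm that the database shows which courses were ongoing. If it does not, obtain that item by query; until then, present the plain summary only as observed duration to the cut.

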8.2. Secondary objectives

- To evaluate the treatment outcomes of avelumab plus axitinib as first-line therapy for patients with mRCC in a real-world setting, as determined by the following endpoints:
 - Real-world PFS.
 - Overall survival (OS).
 - Objective response rate (ORR).
 - Best overall response (BOR) for primary lesions.
 - Time to treatment discontinuation (TTD) of avelumab plus axitinib as first-line therapy.
- To describe the treatment patterns for avelumab plus axitinib as first-line therapy in a real-world setting.
- To describe the clinical use of corticosteroids for immune-related adverse events (irAEs) occurring during the course of administering avelumab plus axitinib combination therapy.
- To describe the pre-treatment and treatment of infusion-related reactions caused by avelumab.
- To describe the subsequent treatment of avelumab plus axitinib combination therapy.

CCI

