### 4 ANALYSIS SETS/POPULATIONS

#### 4.1 FULL ANALYSIS SET (FAS)

*The FAS will comprise patients who meet the inclusion criteria and do not meet the exclusion criteria.*

Inclusion criteria

- 1) *Diagnoses of mRCC based on the General Rule for Clinical and Pathological Studies on RCC (Fifth Edition) before the administration of avelumab plus axitinib*

PFIZER CONFIDENTIAL

as first-line therapy. Patients with *mRCC* presenting with unresectable disease, either a unresectable locally advanced or metastatic disease.

- 2) Age over 18 years at the time of the first administering of avelumab plus axitinib as first-line therapy for *mRCC* (baseline).
- 3) Index date from December 20, 2019, to October 17, 2022.

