**【Division of categorical variables】**

Factor	Category
Performance of nephrectomy after avelumab plus axitinib combination therapy	No; Yes
Presence or absence of second-line therapy	No; Yes; Unknown
Drug category	TKI; mTOR; IO; Other

mTOR, mammalian target of rapamycin; IO, immunotherapy; TKI, tyrosine kinase inhibitor.

CCI

PFIZER CONFIDENTIAL

CCI

CCI	[REDACTED]
[REDACTED]	[REDACTED]

PFIZER CONFIDENTIAL

CT24-WI-GL03-RF03 2.0 *Non-Interventional Statistical Analysis Plan For Secondary Data Collection*  
Study 01-Jun-2020  
Page 29 of 30

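### SAP 7.2.2.10 gives second-line therapy as a percentage of the whole FAS and efficacy set, mixing patients still on first-line at the cut with patients who ended it

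*SAP*

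**What the plan says.** Protocol 8.2 sets the secondary objective: "To describe the subsequent treatment of avelumab plus axitinib combination therapy". Protocol Table 1 specifies the data for it as the name and duration of use of second-line drugs.

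For the endpoint "Presence or absence of second-line therapy", SAP 7.2.2.10 defines the population as "Source : FAS, Efficacy analysis set". The method is "A frequency table (number of cases, percentage (%)) will be created for categorical variables". The category table under that section reads "Presence or absence of second-line therapy No; Yes; Unknown". The section also summarises, as a continuous variable, "The period from the end date of first-line therapy to the beginning of second-line therapy (days"), and plans it by reason for termination as well.

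The FAS admits any patient with "Index date from December 20, 2019, to October 17, 2022", and SAP 2.1 explains the last date: "To ensure a two-week follow-up period, patients with an index date between December 20, 2019, and October 17, 2022, will be included". Observation ends for everyone on 31 October 2022. The efficacy set (SAP 4.3) requires an index date before 30 April 2022.

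Nothing legible in the SAP states the denominator of the second-line percentage beyond the named source population, or says how a patient still on first-line is to be coded. The sections for table shells and further endpoint definitions are marked not applicable. Redacted text follows 7.2.2.10 and cannot be assessed.

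**The concern.** A patient can only move to second-line after first-line ends. As the table is laid out, No covers three different situations: first-line still running at the cut, first-line ended with nothing further started, and death without a second line. Only the last two say anything about what follows avelumab plus axitinib. Some FAS patients have only two weeks of observation.

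The SAP makes the needed distinction elsewhere. The real-world PFS censoring rules in SAP 5.1 separate ongoing first-line, ended first-line without second-line, and second-line started. The TTD tables in 7.2.2.6 have a category for ongoing treatment. Section 7.2.2.10 does not carry this over.

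At stake is how the headline second-line percentage is read. Clinicians will tend to take it as the proportion of patients who receive further treatment once the combination stops. Protocol section 7 also places this study second in a series of three with different follow-up lengths. A percentage of all enrolled patients will rise along that series even if practice does not change.

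**Working it through.** The documents state no expected second-line percentage, so there is no planned figure to reproduce.

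**Inputs from the documents.** Index dates run from 20 December 2019 to 17 October 2022 (FAS), or to 29 April 2022 as the last day before 30 April (efficacy set). The cut is 31 October 2022. A month is 30.4375 days and durations count the start day (SAP section 5). About 150 patients are expected (protocol 9.5).

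**Assumptions.** Accrual is uniform and time on first-line is exponential. No expected time on first-line is given. The phase 3 median PFS of 13.8 months quoted in protocol section 7 serves as a proxy, with 8 and 18 months on either side.

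**Step 1, potential follow-up.**
- Longest, both sets: 1,047 / 30.4375 = 34.40 months.
- Shortest, FAS: 15 / 30.4375 = 0.49 months.
- Shortest, efficacy set: 186 / 30.4375 = 6.11 months.

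**Step 2, what the crude percentage measures.** Let N be all patients, E those who ended first-line by the cut, and S those who started second-line by the cut. The table gives S/N and uptake after first-line is S/E. Their ratio is E/N = 1 − p, where p is the share still on first-line. Setting unknowns aside, this holds whatever the uptake is.

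**Step 3, illustrative p.** With L = ln 2 / median, p = [exp(−L·fmin) − exp(−L·fmax)] / [L·(fmax − fmin)].

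At 13.8 months, L = 0.05023:
- FAS: (0.9756 − 0.1777) / (0.05023 × 33.91) = 0.469, about 70 of 150.
- Efficacy set: (0.7357 − 0.1777) / (0.05023 × 28.29) = 0.393. Its expected size is 150 × 862/1,033, about 125, so about 49 patients.

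| Median on first-line (months) | FAS: p | FAS: 1 − p | Efficacy set: p | Efficacy set: 1 − p |
|---|---|---|---|---|
| 8 | 0.309 | 0.691 | 0.220 | 0.780 |
| 13.8 | 0.469 | 0.531 | 0.393 | 0.607 |
| 18 | 0.548 | 0.452 | 0.481 | 0.519 |

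If accrual may also be front- or back-loaded and the median is 8 to 24 months, p runs from 18% to 73% in the FAS and from 14% to 65% in the efficacy set.

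**Step 4, effect on the table.** This step is a simulation with a 13.8-month median, an assumed 60% of patients going on to second-line, and an assumed exponential gap with mean 1 month.
- FAS: crude about 31%, against about 57% among patients who ended first-line.
- Efficacy set: crude about 35%, against about 58%.
- Cumulative incidence of second-line from the index date: about 26% at 12 months and 41% at 24 months.

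The two crude figures differ only because the efficacy set has longer minimum follow-up. The percentage among those who ended first-line barely moves.

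**Step 5, the gap variable.** It exists only for patients who had started second-line by the cut, so longer gaps are more often lost. At a 13.8-month median the observed mean gap is about 4% to 5% short if the true mean is 1 month, and about 14% short if it is 3 months.

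**The case against.** The strongest reply is that the objective is only descriptive. The plan names no uptake rate, and a percentage of all patients correctly reports who had received second-line by 31 October 2022. Step 4 supports this: the crude figure lies between the 12- and 24-month cumulative incidence, so it is not below every sensible measure. This stands. A reader might infer that the plan heavily understates uptake, but that needs a target the documents do not set and an uptake figure they do not give.

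A reader might also infer that the study cannot answer its subsequent-treatment objective. It can in part. Drug category, regimen and second-line duration match what protocol Table 1 asks for, and patients still on first-line do not alter the mix of drugs among starters.

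It can also be said that first-line status is reported elsewhere. Section 7.2.2.7 tabulates termination of each drug in both sets and plans a swimmer plot, and 7.2.2.6 counts combination TTD events and ongoing treatment. This helps only partly. The termination tables are per drug, so the number who ended both cannot be read from them. The combination TTD table covers the efficacy set only. Neither is crossed with second-line status.

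Finally, coding ongoing patients as No is an inference. They might be left blank or set to Unknown, since no rule is visible. That is fair, but it makes the denominator less clear, not more.

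**Conclusion.** The concern holds as a problem of denominator and layout. The second-line percentage covers the whole FAS and efficacy set, and as laid out it does not separate patients not yet at risk of second-line from those who ended first-line. It should be read only as second-line started by the cut. It is below uptake among patients who ended first-line by the factor 1 − p, and it grows with follow-up.

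The size of p cannot be derived from the documents. The ranges of 31% to 55% (FAS) and 22% to 48% (efficacy set) rest on uniform accrual, exponential time on first-line and assumed medians of 8 to 18 months. PFS is also not the same as time on treatment. They show that the share is probably substantial and do not predict it. The bias in the gap variable is towards short values and is modest if gaps are short.

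This is a worthwhile clarification of a descriptive secondary analysis. It does not touch the primary objective or the time-to-event endpoints.

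**What to change.** In SAP 7.2.2.10:

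1. Replace the No/Yes/Unknown table with five rows in each analysis set: first-line ongoing; ended and second-line started; ended, alive, none started; died without second-line; unknown.
2. Add the percentage starting second-line among patients who ended both drugs, preferably also by reason for termination, because stopping for efficacy is one of the listed reasons. State how deaths on first-line are counted.
3. Identify patients who ended both drugs from the recorded termination status of each drug. Do not use the TTD end date in SAP 5.1: it is capped at the data cut, so a patient still on treatment could appear to have ended on or before that date.
4. Keep drug category and regimen as percentages of patients who started second-line. Using everyone who ended first-line would mix non-starters into the drug distribution.
5. State that the gap from first-line to second-line is observed only in patients who had started by the cut and so is biased somewhat short. A cumulative incidence of second-line from the end of first-line, with death as a competing event, is an optional addition.

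The cost is SAP wording and one derived flag. The termination status, dates and deaths needed are already used in other planned analyses. The downside is a smaller denominator, and so less precision, for the added percentage. It will also still run slightly low, because some patients who ended first-line shortly before the cut will start second-line after it.
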